6.3 Treatment of Adverse Event

Patients who develop any adverse event while on study will receive standard of care treatment. Radiation, cisplatin, and surgery are already standard of care treatments for these patients. Standard of care treatment for known potential adverse events from these treatments are established.

7.0 STATISTICAL CONSIDERATIONS

7.1 Study Design/Study Endpoints

The main objective of this Phase-II trial is to estimate the two-year progression-free survival probability (PFSP) in this group of patients treated with de-escalated radiotherapy. The planned total sample size is 80 patients. (This number was increased to 120 as of July 7, 2017, 140 as of February 7, 2019, 160 as of May 29, 2019, 180 as of October 9, 2019, 200 as of January 7, 2020, and 250 as of June 17, 2020. Please see details below.) The recruitment phase is expected to last 48 monthsDrop out is expected to be about 10%, based on a previous trial (LCCC 1120), hence we expect a total of 225 patients to complete the study.

The statistical aim is phrased as a hypothesis test with the null hypothesis being that the two-year PFSP is 0.93 and the alternative hypothesis being that the two-year PFSP is 0.86 (or less). A one sample binomial test will be used to assess this hypothesis. If the null hypothesis is rejected the conclusion will be that the de-escalated treatment is inferior to the standard treatment. If the null hypothesis is not rejected the conclusion will be that the de-escalated treatment is at least as good as the standard RT.

We give power calculations for two sample sizes. For a sample size of n=73 (patients who complete the study), the null hypothesis will be rejected if 11 or more patients fail. Failure is defined as not reaching the two-year time point progression-free. Defining P(Reject H0) to be the probability of rejecting the null hypothesis, the performance of the test is summarized in the following table.

True 2-year PFSP	P(Reject H0)
0.93	0.03
0.86	0.58
0.80	0.94
0.75	0.99

For a sample size of n=80 patients, the null hypothesis will be rejected if 12 or more patients fail. The performance of the test is summarized in the following table.

True 2-year PFSP	P(Reject H0)
0.93	0.02
0.86	0.57
0.80	0.94
0.75	0.99

For n=73 to 78, the critical point is 11 failures. For n=79 and 80, the critical point is 12 failures. With these critical points, type-I error ranges from 0.023 to 0.045 depending on sample size.

Sample size and power re-calculation: On July 7, 2017, the PI, noticing the higher than expected patient accrual rate, decided to increase sample size to 120. This should result in

about 108 patients to complete the study, after accounting for drop-out with an expected drop-out rate of 10%.

For a sample size of n=108 patients, the null hypothesis will be rejected if 13 or more patients fail. The performance of the test is summarized in the following table.

True 2-year PFSP	P(Reject H0)
0.93	0.04
0.86	0.76
0.80	0.99
0.75	1.00

For n=100 to 101, the critical point is 12 failures. For n=102 to 108, the critical point is 13 failures. With these critical points, type-I error ranges from 0.026 to 0.050 depending on sample size.

Sample size and power re-calculation: On February 7, 2019, the PI, noticing the higher than expected patient accrual rate, decided to increase sample size to 140. This should result in about 126 patients to complete the study, after accounting for drop-out with an expected drop-out rate of 10%.

For a sample size of n=126 patients, the null hypothesis will be rejected if 13 or more patients fail. The performance of the test is summarized in the following table.

True 2-year PFSP	P(Reject H0)
0.93	0.03
0.86	0.79
0.80	0.99
0.75	1.00

For n=120 to 123, the critical point is 14 failures. For n=124 to 128, the critical point is 15 failures. With these critical points, type-I error ranges from 0.030 to 0.050 depending on sample size.

Sample size and power re-calculation: On May 29, 2019, the PI, waiting for the opening of LCCC 1912 and noticing the completion of accruing planned 140 patients, decided to increase sample size to 160. This should result in about 144 patients to complete the study, after accounting for drop-out with an expected drop-out rate of 10%.

For a sample size of n=144 patients, the null hypothesis will be rejected if 16 or more patients fail. The performance of the test is summarized in the following table.

True 2-year PFSP	P(Reject H0)
0.93	0.045
0.86	0.870
0.80	0.99

0.75	1.00
------	------

For n=140 to 143, the critical point is also 16 failures. With these critical points, type-I error ranges from 0.036 to 0.043 depending on sample size.

Sample size and power re-calculation: On October 9, 2019, the PI, waiting for the opening of LCCC 1912 and noticing the completion of accruing planned 160 patients, decided to increase sample size to 180. This should result in about 162 patients to complete the study, after accounting for drop-out with an expected drop-out rate of 10%.

For a sample size of n=162 patients, the null hypothesis will be rejected if 18 or more patients fail. The performance of the test is summarized in the following table.

True 2-year PFSP	P(Reject H0)
0.93	0.003
0.86	0.45
0.80	0.96
0.75	1.00

For n=159 to 161, the critical point is also 18 failures. With these critical points, type-I error ranges from 0.030 to 0.035 depending on sample size.

Sample size and power re-calculation: On January 7, 2020, the PI, waiting for the opening of LCCC 1912 and noticing the completion of accruing planned 180 patients, decided to increase sample size to 200. This should result in about 180 patients to complete the study, after accounting for drop-out with an expected drop-out rate of 10%.

For a sample size of n=180 patients, the null hypothesis will be rejected if 19 or more patients fail. The performance of the test is summarized in the following table.

True 2-year PFSP	P(Reject H0)
0.93	0.048
0.86	0.93
0.80	0.99
0.75	1.00

For n=177 to 179, the critical point is also 19 failures. With these critical points, type-I error ranges from 0.042 to 0.048 depending on sample size.

Sample size and power re-calculation: On June 17, 2020, the PI, waiting for the opening of LCCC 1912 and noticing the completion of accruing planned 200 patients, decided to increase sample size to 250. This should result in about 225 patients to complete the study, after accounting for drop-out with an expected drop-out rate of 10%.

For a sample size of n=225 patients, the null hypothesis will be rejected if 23 or more patients fail. The performance of the test is summarized in the following table.

True 2-year PFSP	P(Reject H0)
0.93	0.045
0.86	0.96
0.80	0.99
0.75	1.00

For n=220 to 224, the critical point is also 23 failures. With these critical points, type-I error ranges from 0.036 to 0.045 depending on sample size.

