1.0 BACKGROUND AND RATIONALE

1.1 Study Synopsis

The proposed study is a follow-up study to LCCC 1120 and 1413. We have observed an excellent pathological complete response rate (LCCC 1120) and progression free survival (PFS) (LCCC 1413) in patients with HPV positive and/or p16 positive low-risk oropharyngeal squamous cell carcinoma (OPSCC) who received de-intensified chemoradiotherapy (CRT). We have shown that de-intensification is efficacious in these two phase II studies. We are leaders in the genomic classification of head and neck cancer, and investigators at LCCC ██████████ have shown that HPV-associated oropharyngeal cancer has a unique genetic profile. A major question is whether we can de-intensify in patients with HPV-associated oropharyngeal cancer who have smoking histories. The aim of the current study is to build upon our two phase II studies and the genomic profiling studies. Our hypothesis is that genomic profiling of patients' tumors (specifically for p53 mutations) will help in triaging patients to de-intensification versus standard of care. We will enroll patients with HPV-associated OPSCC regardless of smoking history and will assess p53 mutational status in patients with a smoking history. We will use the same de-intensification chemoradiotherapy regimen we have already evaluated in LCCC 1120 and 1413 in patients with HPV-associated OPSCC who have a minimal smoking history and in patients with a smoking history but with wild-type p53. If patients with a smoking history have mutated p53 they will not receive de-intensified chemoradiotherapy, but instead will receive standard doses. Our primary objective will be 2 year PFS. In LCCC 1413 the primary null hypothesis was 2 year PFS of 87%. We hypothesize, that by using genomics in the patients with a significant smoking history we will better select those who we can safely de-intensify and that the 2 year PFS will improve to 93%. We will also prospectively assess circulating free HPV DNA (cf-HPV-DNA) from blood samples. This study will be multi-institutional, with patients also enrolling at the University of Florida, Gainesville, Florida; the University of Florida Proton Therapy Institute, Jacksonville, FL; and Rex Cancer Center of Raleigh, Raleigh, North Carolina.

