1.8 Rationale

The proposed study will build upon on our seminal prior phase II and genomic characterization studies by leveraging unique clinical/ translational strengths at UNC-LCCC: cancer genomics and cfHPV-DNA. Our over-arching hypothesis is that the

genomic characterization of OPSCC tumor specimens from patients with > 10 pack year smoking history can be used to help decide whether de-intensification would be efficacious.

Because of the positive results of our first two de-intensification studies (LCCC 1120, LCCC 1413) and the emerging genomic risk stratification data from [REDACTED] et al. and [REDACTED] et al., we are proposing conducting a similar study with the major modification of:

1. Tumor Genetics: Tumor genetics will be assessed in all patients with > 10 pack year smoking history, and select patients with extensive smokeless tobacco history, based on the PI's assessment. The UNC Molecular Genetics Laboratory will perform a mutation panel interrogating selected regions of 26 genes (p53 mutation is the most common to this patient population) using next-generation sequencing. P53 mutational status will be used to assess eligibility of patients with >10 pack years smoking history.
2. Circulating free HPV DNA: In this study we will prospectively collect blood samples pre-treatment, during, and after treatment to evaluate the kinetics of cfHPV-DNA in all patients.
3. Primary endpoint: Our hypothesis is that by using genomic profiling in the patients with HPV-associated OPSCC and > 10 pack year smoking history that we will be better able to select those patients with HPV-associated OPSCC who would safely benefit from de-intensification. The primary endpoint is PFS, however by using genomics to select the most favorable patients with a > 10 pack year smoking history, we estimate the PFS to be 93% (for the entire population, regardless of smoking), instead of the 87% as has been reported in previous studies¹⁰ and our prior studies.

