3.0 ENDPOINTS

3.1 Primary Endpoint

Patients with HPV-positive and/or p16-positive OPSCC will receive de-intensified CRT. The 2 year PFS will be evaluated. Our null hypothesis (H_0) is that the PFS rate is 93% and our alternate hypothesis (H_1) is that the PFS rate is 86%.

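### Section 7.1 does not settle whom the primary test covers: n=225 and the 23-failure rule come from all enrolled patients, but both conclusions are about the de-escalated treatment alone

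*Combined protocol and SAP*

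**What the plan says.** **Who is treated how.** Enrolment is open whatever the smoking history (1.1), and a p53 mutation is not an exclusion (4.2). Section 1.1 states: "If patients with a smoking history have mutated p53 they will not receive de-intensified chemoradiotherapy, but instead will receive standard doses". Sections 5.1, 5.6 and 5.7 give these patients 70 Gy and one additional weekly chemotherapy dose, and they remain on study.

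**Text pointing to all patients.** Section 7.1 records that the investigator "decided to increase sample size to 250" and, after 10% dropout, "hence we expect a total of 225 patients to complete the study". Nothing is deducted for p53-mutated patients. In section 1.8 the benchmark reads "we estimate the PFS to be 93% (for the entire population, regardless of smoking". The schema caption in 5.1 describes the objective as PFS after treatment guided by genetic risk.

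**Text pointing to de-intensified patients only.** Section 7.1 aims to "estimate the two-year progression-free survival probability (PFSP) in this group of patients treated with de-escalated radiotherapy". Section 3.1 says "Patients with HPV-positive and/or p16-positive OPSCC will receive de-intensified CRT" and then names 2-year PFS. Section 5.11 describes the endpoint as PFS after de-intensified CRT.

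**The decision.** "A one sample binomial test will be used to assess this hypothesis". The null is 0.93 and the alternative 0.86 or less. With n=225, the null is rejected at 23 or more failures. Rejection means the de-escalated treatment is inferior to standard; non-rejection means it is at least as good.

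**The one explicit exclusion.** Section 7.2 leaves p53-mutated patients out of the log-rank comparison by smoking history. It says nothing similar about the main test.

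**The concern.** Two readings are possible, and each leaves one part of the plan that does not fit.

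- **All completers are tested.** Sample size, cut-off and benchmark then agree with each other, but the conclusion does not follow. Patients given the dose that the protocol itself calls standard would be counted in deciding whether the reduced dose is inferior to standard. Poor results at 70 Gy could make 60 Gy look inferior, and good results at 70 Gy could hide excess failures at 60 Gy.
- **Only de-intensified patients are tested.** The conclusion then fits, but fewer than 225 patients would be available from 250 enrolled, the cut-off may change, and the 93% was not set for this subset.

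In a single-arm trial decided by a fixed failure count, an undefined analysis set also leaves the choice open until failures are known.

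**Working it through.** **Inputs from the documents:** null failure probability 0.07; alternative 0.14; 250 enrolled; 10% dropout; cut-off 23 (all section 7.1).

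**Assumed, because the documents give no figure:** a p53-mutated share of completers of 2, 5, 10 or 15% (m = 4, 11, 22 or 34 of 225), and 2-year PFS at 70 Gy of 80-90%. As a favourable case, 97% at 70 Gy is also used.

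**Step 1. The plan's own figures.** 250 × 0.90 = 225. With X ~ Binomial(225, p):
- P(X ≥ 23 | p = 0.07) = 0.0446, stated as 0.045.
- P(X ≥ 23 | p = 0.14) = 0.963, stated as 0.96.

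Both reproduce, and 23 is the smallest cut-off with one-sided error at or below 0.05. The arithmetic for n=225 is sound. What is unclear is which patients make up the 225.

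**Step 2. All completers tested, verdict read as concerning 60 Gy.** Total failures are Binomial(225−m, p60) + Binomial(m, p70), and the null is rejected at 23 or more. With 60 Gy PFS truly 93% (p60 = 0.07):

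| Share (m) | 70 Gy PFS 90% | 70 Gy PFS 80% |
|---|---|---|
| 2% (4) | 0.048 | 0.059 |
| 5% (11) | 0.054 | 0.093 |
| 10% (22) | 0.064 | 0.170 |
| 15% (34) | 0.077 | 0.283 |

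The stated value is 0.045. If the 70 Gy patients also have 93% PFS, the result is 0.045 at every share.

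**Step 3. The same test if 93% holds for the whole population.** With 70 Gy PFS at 80%, the 60 Gy failure probability must satisfy (225−m)·p60 + 0.20·m = 0.07 × 225 = 15.75. For m = 22, p60 = (15.75 − 4.4)/203 = 0.0559. Rejection probabilities for m = 11, 22 and 34 are then 0.041 to 0.044, so there is no inflation.

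**Step 4. The other direction.** With 60 Gy PFS at the alternative of 86% and 70 Gy PFS at 97%, pooled power is 0.94, 0.91 and 0.86 for m = 11, 22 and 34, against 0.963 when all fail at 14%.

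**Step 5. Test restricted to de-intensified patients.** The cut-off is the smallest k with P(X ≥ k | n, 0.07) ≤ 0.05:

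| Share | n | Cut-off | Type I error | Power at 86% | Power if 23 is kept |
|---|---|---|---|---|---|
| 2% | 221 | 23 | 0.038 | 0.954 | 0.954 |
| 5% | 214 | 22 | 0.046 | 0.957 | 0.933 |
| 10% | 203 | 21 | 0.048 | 0.950 | 0.887 |
| 15% | 191 | 20 | 0.047 | 0.939 | 0.810 |

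At 2% the cut-off does not change. From 5% upward, keeping 23 on the smaller set costs power, and re-deriving it recovers most of the loss.

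**The case against.** A reader might infer that the primary test is applied to everyone enrolled and that its type I error is therefore inflated. The documents do not support either statement as fact. No section says that all enrolled patients are analysed. The rule is set on expected completers, not on the 250 enrolled, and the aim in 7.1 names only patients treated with de-escalated radiotherapy. The inflation in step 2 appears only when the 93% is moved to the 60 Gy subset. Sections 1.6 and 1.8 attach it to patients regardless of smoking, and on that basis step 3 shows none.

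The share may also be small. Section 1.6 describes p53 mutations as rare, if present at all, in HPV-associated disease, and current smokers are now excluded (4.2.7). At 2% the effect is slight.

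Finally, an all-patient test with a conclusion about p53-guided selection would be coherent and would need no new cut-off. Changing the primary set now carries its own risk: the current version is dated August 2023, about three years after the last sample size increase.

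All of this stands as a limit on the size and wording of the point. It does not remove the inconsistency. On the all-patient reading the two conclusions in 7.1 still name the wrong object, and on the restricted reading n=225 is still the wrong number.

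**Conclusion.** The plan is inconsistent about the population of its primary test, and no reading reconciles sections 1.8, 3.1, 5.11 and 7.1. The defect concerns the definition of the analysis set and the wording of the conclusion. It is not a demonstrated error rate, and sample size is not the main issue: once the cut-off is re-derived, power at 86% stays at about 0.94-0.96 for shares up to 15%.

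The consequence ranges from negligible (0.048-0.059 against 0.045 at a 2% share) to substantial (up to 0.283 at 15% with 80% PFS at 70 Gy). Those figures rest on three assumptions that the documents do not supply: the p53-mutated share, PFS at 70 Gy, and 93% holding for 60 Gy patients alone. If 93% holds for the whole population, the all-patient test keeps its error rate and only its conclusion is misdirected. This should be fixed, because it decides what the primary result may be said to show.

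**What to change.** In 3.1 and 7.1, state the primary analysis set and match cut-off and conclusion to it. Make and document the decision without reference to outcome data.

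- **For a verdict on the de-escalated treatment:** test only patients assigned the de-intensified regimen. Define the set by assigned regimen and not by pack years. Section 5.1 also sends selected smokeless-tobacco users for testing, and a mutated one with 10 or fewer pack years would slip into a set defined by smoking history. Exclude every patient assigned 70 Gy.
- **Cut-off:** re-derive it by exact binomial for the realised n (for example 23 at 221, 22 at 214, 21 at 203, 20 at 191).
- **Benchmark:** say openly that 93% is carried over to this subset as an assumption.
- **70 Gy group:** report its 2-year PFS separately with a confidence interval.
- **All patients:** also report the result under the existing rule (23 of 225), with its conclusion worded for the p53-guided strategy.

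The cost is wording, a re-derived cut-off, and a fall in power at 86% from 0.963 to between 0.939 and 0.957 over the shares examined. It is a late change to the analysis set, so the date, the reason and the absence of access to outcomes need to be recorded. No further patients or data are required.

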1.2 Standard of care CRT for OPSCC

The standard treatment regimen for HPV-associated oropharyngeal or unknown primary squamous cell carcinoma of the head and neck is 70 Gy, 2 Gy per day, 35 fractions, over 7 weeks with 2 to 3 doses of cisplatin 100mg/m². Most institutions perform a PET/CT at 10 to 16 weeks after CRT to assess response. Depending on the clinical response, patients may have to have a biopsy of the primary site and/or a neck dissection after treatment. Typically patients with a negative PET/CT scan are observed (i.e. no surgery). Standard CRT is associated with significant acute toxicity with most patients experiencing grade 3 and 4 acute toxicity during treatment. Furthermore, approximately 20% of patients will have Grade 3-4 long-term morbidity related to their definitive CRT.

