1.6 Genomic characterization of HPV-associated and Tobacco-associated Oropharyngeal cancer

[figure not shown]
HPV- associated OPSCC has a different genomic profile as compared to HPV-negative, tobacco associated OPSCC³⁵. Seminal work done by Dr. [REDACTED] using the tumor cancer genome atlas has shown that HPV-negative tobacco associated OPSCC characteristically has p53 mutations and CCND1 amplifications. These genetic alterations are rarely (if ever) seen in HPV-associated OPSCC, especially those with minimal smoking histories. Dr [REDACTED] et al. have further characterized the tumor genomic profiles in patients with HPV- associated OPSCC with significant smoking histories ($>$ 10 pack years). They observed that not all HPV-associated OPSCC are the same on the genetic level, especially in those with $>$ 10 pack year smoking history [REDACTED] et al. used next-generation sequencing to analyze genetic mutations in 66 HPV-positive oropharyngeal cancer patients, who were also categorized into groups based on smoking history. They found that disease-free and overall survival were better in the less than 10-pack year group, and there were differences in mutations between the two groups based on smoking history. Mutations in genes such as TP53, CDKN2A, KRAS and NOTCH1 almost exclusively observed in the $>$ 10 pack-year group while HLA-A mutations were almost exclusively in the lighter smoking group. These data provide a molecular criteria based

on genomic mutations to help better stratify risk/prognosis and potentially to guide treatment selection, namely whether de-intensification should be used.

The proposed study aims to build upon the work of [REDACTED] et al. and [REDACTED] et al. by evaluating whether genomic profiling can be used to better select patients for de-intensification. By better selecting patients (using genomic profiling, see below) for de-intensification, we hypothesize that we can further improve the 2 year PFS to 93% for patients with HPV- associated OPSCC regardless of smoking history.

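### Section 7.1 words a single-arm test of 93% against 86% as a verdict against standard treatment, but neither figure is given anywhere as the standard-treatment PFS

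*Combined protocol and SAP*

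**What the plan says.** Section 3.1 sets the hypotheses: "Our null hypothesis (H_0) is that the PFS rate is 93% and our alternate hypothesis (H_1) is that the PFS rate is 86" per cent. Section 7.1 repeats them as 0.93 and 0.86 or less, uses a one-sample binomial test with no control arm, and attaches two conclusions:

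- on rejection, "If the null hypothesis is rejected the conclusion will be that the de-escalated treatment is inferior to the standard treatment";
- otherwise, "If the null hypothesis is not rejected the conclusion will be that the de-escalated treatment is at least as good as the standard RT".

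The current design in Section 7.1 expects 225 completers out of 250 and rejects at 23 or more failures. The same cut-off is printed for n=220 to 224.

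The background sections show where the figures come from:

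- **93%.** Section 1.1 expects "that the 2 year PFS will improve to 93" per cent through genomic selection. Section 1.6 says "we hypothesize that we can further improve the 2 year PFS to 93" per cent. Section 1.8 estimates 93% for this trial's whole population, "instead of the 87% as has been reported in previous studies¹⁰ and our prior studies".
- **86%.** It appears only as the alternative hypothesis, in Sections 3.1 and 7.1.
- **87%.** Section 1.1 states "In LCCC 1413 the primary null hypothesis was 2 year PFS of 87" per cent. This figure plays no part in the Section 7.1 rule.
- **Standard treatment.** Section 1.2 describes it ("The standard treatment regimen for HPV-associated oropharyngeal or unknown primary squamous cell carcinoma of the head and neck is 70 Gy", with cisplatin) and gives no PFS for it.

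**The concern.** A one-sample test compares the observed rate with the number written into the null hypothesis and with nothing else. A verdict against standard treatment follows only if that number is the standard-treatment rate. Here it is the trial's own target. Missing a target is not inferiority to 70 Gy, and failing to show that the target was missed is not parity with 70 Gy.

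The two sentences are the interpretation the plan fixes in advance for its hypothesis test. A report that followed them would claim parity with, or inferiority to, a comparator that was neither enrolled nor given a PFS figure. In a de-escalation trial that is the claim readers are most likely to carry forward.

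**Working it through.** **1. Inputs.** From Section 7.1: null PFS 0.93, alternative 0.86, 10% drop-out, n=225, rejection at 23 or more failures. Check on n: 250 × 0.90 = 225.

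**2. Reproduce the printed figures.** Let X be the number of failures, X ~ Binomial(225, 1 − PFS). The probability of rejection is P(X ≥ 23).

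- At PFS 0.93: 0.0446 (printed 0.045).
- At PFS 0.86: 0.9628 (printed 0.96).
- For n=220 to 225 at PFS 0.93: 0.036 to 0.045, as printed.

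The cut-off and its stated error rates are sound at this n.

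**3. What each outcome supports.**

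- Rejection: 23 or more failures has probability 0.0446 at PFS 0.93 and less at any higher PFS. It supports *2-year PFS is below 93%*, one-sided error 0.045.
- Non-rejection: P(X ≤ 22) at PFS 0.86 is 1 − 0.9628 = 0.0372, and less at any lower PFS. It supports *2-year PFS exceeds 86%*, one-sided error 0.037.

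Neither statement contains a standard-treatment rate.

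**4. Look for a standard-treatment rate.** Section 1.2 gives none. Section 1.4 contains 93% twice, once as 3-year overall survival in a low-risk group and once as a distant-metastasis result; neither is 2-year PFS. Section 1.8 attributes the 87% jointly to reference 10 and to the group's own prior studies, and Section 1.5 describes those studies as de-intensified. So 87% is a historical figure of mixed origin that is not labelled as the standard rate.

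**5. Would supplying a benchmark rescue the wording?** With n=225 and the cut-off at 23:

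| True 2-year PFS | P(rejected, so called inferior) | P(not rejected, so called no worse than standard) |
|---|---|---|
| 0.93 | 0.045 | 0.955 |
| 0.92 | 0.136 | 0.865 |
| 0.91 | 0.292 | 0.708 |
| 0.90 | 0.488 | 0.512 |
| 0.88 | 0.821 | 0.179 |
| 0.87 | 0.913 | 0.087 |
| 0.86 | 0.963 | 0.037 |

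- *If 93% were the standard rate:* a regimen truly at 91% would pass with probability 0.71, and one at 90% with probability 0.51. Non-rejection would not show parity with 93%.
- *If 87% were the standard rate:* a regimen exactly matching it would be called inferior with probability 0.91.

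**6. The boundary results.** 22 failures gives 203/225 = 90.2% (exact 95% CI 85.6 to 93.8) and is called no worse than standard. 23 failures gives 202/225 = 89.8% (85.1 to 93.4) and is called inferior. The two intervals nearly coincide, while the prescribed conclusions are opposite.

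**The case against.** The strongest defence has three parts.

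First, the test is informative. Non-rejection at n=225 is more than absence of evidence, because it excludes PFS of 86% or less at one-sided 0.037. This stands, and it is why the cut-off should be kept and the favourable statement put in those terms.

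Second, the 0.91 is an error rate only if 87% is what standard treatment achieves in this population. A reader might infer that the plan would condemn a regimen equal to standard treatment nine times in ten. The documents do not support that. They never call 87% the standard-treatment rate, they attribute it partly to the group's own de-intensified studies, and what reference 10 reported cannot be checked from the documents. If 93% is simply the target for a selected population, rejecting at a true 87% is intended power, close to the printed 0.96 at 0.86. The objection stands, so the 0.91 is conditional. It does not restore the wording, because on that reading rejection means only that the target was missed.

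Third, Section 7.1 describes the main objective as estimating 2-year PFS, and Section 2.1 frames the primary hypothesis differently, around smoking history and p53 status. It would therefore be too strong to say that the whole primary result hangs on these two sentences. The estimate, cut-off and error rates do not depend on them. They are still the stated interpretation of the test, and they remain unsupported.

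**Conclusion.** Wrong as written, in wording rather than in arithmetic. At n=225 the rule separates PFS below 93% (one-sided error 0.045) from PFS above 86% (one-sided error 0.037). It says nothing about standard treatment, because neither value is given as a standard-treatment rate in the text available for review.

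The conclusion does not depend on which benchmark a reader prefers. Taking 93% as standard leaves a 0.51 chance of calling a true 90% no worse than standard. Taking 87% as standard gives a 0.91 chance of calling an equal regimen inferior, a figure that holds only under that assumption. All these probabilities assume 225 completers, each classified as failed or progression-free at two years.

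**What to change.** 1. Keep the printed cut-off: 23 or more failures at n=220 to 225.
2. In Section 7.1 replace the two conclusions with *2-year PFS is below 93%* (rejected) and *2-year PFS exceeds 86%* (not rejected), each with its exact one-sided error at the actual n. Over n=220 to 225 the error at 0.93 runs from 0.036 to 0.045 and the error at 0.86 from 0.049 to 0.037. Delete both comparisons with standard treatment.
3. Report the 2-year progression-free proportion among the patients in the binomial test with an exact (Clopper-Pearson) interval. Separately, report the 2-year estimate from the Kaplan-Meier curve already planned in Section 7.2 with its own interval. The two use censored patients differently and should not share an interval.
4. If 87% is shown, give it as context with its source. Because 86% lies below 87%, say that the favourable statement does not show that PFS matches or exceeds 87%.
5. If completers fall outside 220 to 225, the plan prints no cut-off for this design. Say openly that the one used comes from a rule inferred from the printed ranges for n=100 and above: the smallest failure count with type I error at most 0.05 at PFS 0.93. That rule does not reproduce the cut-offs printed for n=73 to 80. Print the exact errors at both 0.93 and 0.86. Just below n=220 the error at 0.86 passes 0.05 (0.051 at n=219, 0.060 at n=216).

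The cost is two rewritten sentences and two intervals. No patients are added and no printed cut-off moves, so no result at n=220 to 225 changes side. That matters because this version is dated August 2023 and outcomes may already be known. The downside is a more modest favourable conclusion, with no claim against standard treatment.
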